1.1 Primary Outcome

1.1.1 Primary Analysis of Primary Outcome.

The primary aim is to determine if a 16-week intervention based on aerobic conditioning, specificity of training, and muscle overload for strengthening (the PUSH intervention) is more successful in producing community ambulation at 16 weeks post-randomization than an intervention of transcutaneous electrical nerve stimulation, flexibility, and AROM exercises (the PULSE intervention). Therefore, the one-sided null hypothesis that the PUSH intervention does not result in a higher proportion of community ambulators 16 weeks post-randomization will be tested. This hypothesis will be tested at five time points based on a Z-statistic (which is equivalent to the square root of the Pearson chi-square statistic). The critical values for each time point were chosen to preserve an overall type-1 error rate of 0.025. Table 1 shows the critical values:

Table 1. Critical Values for Each Planned Analysis

Analysis	Expected % of information available	Critical z-value for upper-bound alpha spending (for efficacy)	Critical z-value for lower bound alpha spending (for inefficacy/harm)
First interim analysis	28.6%	3.09	-1.76
Second interim analysis	40%	3.03	-1.57
Third interim analysis	60%	2.69	-0.97
Fourth interim analysis	80%	2.37	-0.21
Final analysis	100%	2.03	2.03

If the exploratory analyses reveal data sparseness (expected frequency less than 5 for at least one combination of treatment group and community ambulation status), Fisher's exact test will be performed instead of using the chi-square statistic. A 95% confidence interval will be constructed for the probability of community ambulation in each group by inverting two one-sided tests based on the binomial distribution. If the primary analysis p-value is based on the Z-statistic, then a confidence interval for the difference in community ambulation between the two groups will be constructed using standard asymptotic methods. If the primary analysis is based on Fisher's exact test, then an exact 95% confidence interval will be constructed for the difference in probabilities using the method of Chan and Zhang (Chan ISF, Zhang Z 1999) as implemented in SAS.

The binary outcome variable will be ability to walk at least 300 meters in six minutes (yes/no). This variable will take the value of 'yes' if the participant was tested with the SMWT and walked

300 m or more in six minutes. This variable will take the value of 'no' if 1) the participant was tested with the SMWT and walked less than 300 m in six minutes or 2) the participant was not tested with the SMWT (or the participant was tested but not according to protocol) and adjudication resulted in the participant's being classified as a treatment failure (see 11.5 for description of the adjudication procedure). Participants whose adjudication result is 'indeterminate' will be excluded from the primary analysis.

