The target sample size is 210 randomized hip fracture patients across three clinical sites (with approximately 35 in each treatment group at each site). Study inclusion criteria are: 1) Closed, non-pathologic, minimal trauma hip fracture with surgical fixation; 2) Age 60 or older at time of randomization; 3) Living in the community at time of fracture and at time of randomization; and 4) Ambulating without human assistance during the two months prior to fracture. Participants for whom it is not safe to participate in the interventions will be excluded, as will those who are very unlikely to benefit and in whom the interventions are not feasible.

Section 2: Participating Clinical Sites

Arcadia University (1)

[name], PT, GCS
Clinical Site PI
[name]
[name]
[contact]
[contact]
[contact]

University of Maryland Baltimore (2)

[name]
Clinical Site PI
[name]
[name]
[contact]
[contact]
[contact]

University of Connecticut Health Center (3)

[name]
Clinical Site PI
UConn Health Center
[name]
[name]
[contact]
[contact]
[contact]

Section 3: Study Organization

The Community Ambulation Project (CAP) is a multi-center clinical trial with a Clinical Coordinating Center (CCC) and Data Coordinating Center (DCC) at the University of Maryland Baltimore, an Economic Evaluation Core (EEC) at Dartmouth College, and three clinical sites. In addition to these units, the project will have a Steering Committee (SC) and three Scientific Oversight Committees (SOCs) that will provide expertise needed to conduct this investigation. There will also be a sub-committee that includes a group of experts who will provide support on exercise and nutrition in older adults. A project Organizational Chart is provided in section 3.3. Each clinical site will be affiliated with a university (University of Maryland Baltimore, Arcadia University, and University of Connecticut) and will be recruiting older adults who have experienced a hip fracture in their surrounding geographic areas. All key personnel have collaborated on the design of this trial; most will have multiple roles in its execution, based on individual areas of expertise. Please see Section 20: for a complete Study Team Roster.

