6.2 Randomization

Randomization will occur up to 26 weeks after admission to the hospital for a hip fracture. The randomization schedule for each clinical site will ensure that treatments are randomly assigned within blocks of 2, 4, 6, or 8, with equal numbers of participants assigned to each treatment within each block. Block sizes (two to eight participants per block) will be randomly selected with the probability of each block size specified by DCC staff.

To ensure that those performing evaluations remain blinded to treatment assignment, randomization will only be performed by appropriate unblinded study personnel who have received training and certification on randomization procedures. The clinical site PI, clinical site coordinator, or another unblinded designee will perform the randomization. Random treatment assignments will be obtained using a secure Web-based randomization system. Each member of the study staff who has permission to randomize participants will be assigned a unique, nontransferable user ID that will be required to obtain random treatment allocations. The study staff member will access the system by login on a secure (encrypted) Web site and receive the treatment assignment after responding to prompts confirming that the participant meets all inclusion and exclusion criteria and has given informed consent for enrollment. A printable report will be available as part of the Web system. Site staff will be instructed to print the report and retain it in the participant's binder. Access to the binders is limited to the clinical site PI and coordinator. The date of randomization will mark the start of follow-up for each participant; a computer record is maintained for each attempt to randomize a participant. The clinical site coordinator will inform participants of their group assignment and will tell them when their PT sessions will begin. The coordinator will also provide the name of the PT who will be contacting them. The coordinator will then alert the assigned PT who will contact the participant to schedule the first intervention visit.

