In a secondary analysis, an alternative outcome variable will be created to represent the participant's community ambulation status at 16-week follow-up. This secondary variable will take the value of 'yes' if the participant was tested with the SMWT and walked 300 m or more in six minutes. The secondary variable will take the value of 'no' if 1) the participant was tested with the SMWT and walked less than 300 m in six minutes, 2) the participant was not tested with the SMWT and adjudication resulted in the participant's being classified as a treatment failure because of death, sickness, or gait speed < 0.6 m/s, or 3) the participant was tested with the SMWT but not according to protocol and adjudication resulted in the participant's being classified as a treatment failure, whatever the reason. The secondary variable will take the value of 'missing' if 1) the participant was not tested with the SMWT and adjudication resulted in the participant's being classified as a treatment failure based only on self- or proxy-reported walking limitation or 2) the participant was not tested with the SMWT (or the participant was tested but not according to protocol) and adjudication resulted in the participant's being classified as 'indeterminate'. All participants, including those with a missing value for the alternative outcome variable, will be included in the secondary analysis. To be consistent with the principle of ITT, weighted estimated equations (described below) will be used for this analysis.

Study site will be investigated as a modifier of the effect of the intervention by testing a site-by-intervention interaction term. If study site is an effect modifier, we will report 1) site-specific treatment effects and 2) a summary measure of treatment effect using standardization. Standardization will be accomplished using inverse probability of treatment weighting (as a function of study site) in a marginal structural model.²⁰⁷

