1.1.2 Secondary Analyses of Primary Outcome

In a secondary analysis, an alternative outcome variable will be created to represent the participant's community ambulation status at 16-week follow-up. This secondary variable will take the value of 'yes' if the participant was tested with the SMWT and walked 300 m or more in six minutes. The secondary variable will take the value of 'no' if 1) the participant was tested with the SMWT and walked less than 300 m in six minutes, 2) the participant was not tested with the SMWT and adjudication resulted in the participant's being classified as a treatment failure because of death, sickness, or gait speed < 0.6 m/s, or 3) the participant was tested with the SMWT but not according to protocol and adjudication resulted in the participant's being classified as a treatment failure, whatever the reason. The secondary variable will take the value of 'missing' if 1) the participant was not tested with the SMWT and adjudication resulted in the participant's being classified as a treatment failure based only on self- or proxy-reported walking limitation or 2) the participant was not tested with the SMWT (or the participant was tested but not according to protocol) and adjudication resulted in the participant's being classified as 'indeterminate'. All participants, including those with a missing value for the alternative outcome variable, will be included in the secondary analysis. Weights will be used to adjust for covariate imbalances between the groups due to chance or differential rates of indeterminate outcomes. For the PUSH group, the weight for each observation will be defined as the inverse probability that an observation would be assigned to the PUSH group given the covariates for that observation. This will effectively up-weight observations from groups with lower probability of being in PUSH. Similarly, for the PULSE group, the weight for each observation will be defined as the inverse probability that an observation would be assigned to the PULSE group given the covariates for that observation. The probability of being assigned to PUSH (or PULSE) will be estimated as a function of covariates based on a logistic regression model. Candidate variables for creating the weights will include age, sex, and type of hip fracture; baseline BMI, MNA[®]-SF score, CES-D score, 3MS score, distance walked in six minutes on SMWT, SPPB score, mPPT score, NHATS balance score, gait speed on 50-ft fast walk, and gait speed on 4-m usual walk; and the presence of cardiac disease, pulmonary disease, diabetes, and history of stroke or TIA at baseline. Variables will be ranked for inclusion based on the Beach-Meier approach (Beach 1989). A common rule of thumb for logistic regression models is that there should be at least 10 events and 10 non-events for every covariate in the model. We will follow that rule of thumb (based on the number of community ambulators observed in our sample) in deciding how many covariates to include in the model used to estimate weights.

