1.1.3 Assessment of effect modification by site, period, and patient characteristics

Study site will be investigated as a modifier of the effect of the intervention by testing a site-by-intervention interaction term on the risk difference scale based on a binary regression model

with an identity link. If there is evidence that study site is an effect modifier (i.e., $p < 0.1$ for the interaction term), we will report site-specific treatment effects.

In the fall of 2014, a decision was made to modify the frequency of intervention visits during the first 8 weeks from 3 per week to 2 per week. We will assess the impact of this protocol change on the intervention outcomes in a secondary analysis. To do so, assuming no significant interaction between site and intervention group, we will assess the statistical significance of the interaction between the period during which the participant was randomized (before vs after the protocol change) and treatment group. If there is a significant interaction, then we will make separate treatment group comparisons in the two periods (one comparison for participants randomized during the period when there were three sessions per week and another for participants randomized during the period when there were two sessions per week).

In addition, a series of analyses will be performed to examine the differential impact of the PUSH intervention relative to the PULSE intervention in subgroups defined by participant characteristics. To do this, a variable-by-intervention interaction term will be tested for each of the following variables:

1. Gender
2. Age at baseline (≥ 85 years versus 60-84 years)
3. Baseline depression (CES-D score ≥ 16 versus CES-D score < 16)
4. Baseline balance confidence (with median Activities-Specific Balance Confidence scale score as the cutpoint to define the subgroups)
5. Baseline nutritional status (MNA®-SF score < 8 versus MNA®-SF score ≥ 8)
6. Baseline cognitive status (3MS score < 91 versus 3MS score ≥ 91)
7. Baseline physical performance (SPPB score < 7 versus SPPB score ≥ 7)

If the interaction term for any of these subgroup variables is significant, results will be presented separately in strata of the subgroup variable.

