1.5 Accounting for Variability

To address the possibility that variation between physical therapists could affect the findings, we will rerun the analyses including a random effect for physical therapist. Also, to account for variability between clinical sites, we will run analyses including a random effect for site.

References

Chan, I. S. F. and Zhang, Z. (1999), “Test-Based Exact Confidence Intervals for the Difference of Two Binomial Proportions,” *Biometrics*, 55, 1202–1209

Magder LS, *Controlled Clinical Trials*, 2003 Aug;24(4):411-21.

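### Randomisation is blocked within site, but the primary test and interval ignore site, and the only unconditional site-adjusted overall analysis is a random effect over three sites

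*SAP*

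**What the plan says.** **Design.** Protocol 6.2: "The randomization schedule for each clinical site will ensure that treatments are randomly assigned within blocks of 2, 4, 6, or 8", with equal numbers per arm in each block. The Executive Summary sets the target "across three clinical sites (with approximately 35 in each treatment group at each site".

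**Primary analysis.** SAP 1.1.1 has the hypothesis "tested at five time points based on a Z-statistic (which is equivalent to the square root of the Pearson chi-square statistic", with Fisher's exact test if data are sparse. With the Z-test, "a confidence interval for the difference in community ambulation between the two groups will be constructed using standard asymptotic methods". Neither the test nor the interval mentions site.

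**Where site does appear.**
- SAP 1.5: "to account for variability between clinical sites, we will run analyses including a random effect for site".
- SAP 1.1.3 examines effect modification by "testing a site-by-intervention interaction term on the risk difference scale" and reports site-specific effects if p < 0.1.
- Protocol 15.1 adds an overall summary if site modifies the effect: "Standardization will be accomplished using inverse probability of treatment weighting (as a function of study site) in a marginal structural model". SAP 1.1.3 does not contain it. The SAP's table of changes does not list its removal; for effect modification it says that the protocol gave no details.

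**Where site does not appear.** The weighted secondary analysis in SAP 1.1.2 has a long candidate list ("Candidate variables for creating the weights will include age, sex, and type of hip fracture", then baseline scores and comorbidities), and site is not on it.

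**The concern.** Blocking within site forces the arms to be nearly balanced at each site, so differences in success rate between sites drop out of the treatment difference. A standard error that pools the sites still counts them. It is therefore somewhat too large whenever sites differ, which makes the p-value too large and the interval too wide.

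The planned site-adjusted rerun is a weak remedy for two reasons. A between-site variance from three sites is barely estimable, and when it is estimated as zero the adjustment disappears. Also, a Pearson Z has no place for a random effect, so SAP 1.5 does not say which model is to be fitted to the primary outcome.

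At stake are a small loss of efficiency and the lack of a well-defined overall estimate that respects the randomisation. The validity of the primary conclusion is not at stake.

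**Working it through.** **1. The plan's own power.** Inputs from Protocol 15.6.1: 105 per group, 16% vs 36%, loss 6.8%, non-compliance 12.2%, sequential inflation 2.4%, one-sided 0.025.

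- Effective n per arm = 105 × (1 − 0.068) / 1.024 = 95.6.
- Diluted PUSH rate = 0.16 + 0.20 × (1 − 0.122) = 0.3356, a difference of 0.1756. Mean rate = 0.2478.
- Power = Φ{[0.1756 × √95.6 − 1.96 × √(2 × 0.2478 × 0.7522)] / √(0.16 × 0.84 + 0.3356 × 0.6644)} = Φ(0.87) = 80.8%.

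Table 5 states 80%, so the stated power reproduces for the unstratified test.

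**2. How conservative the unstratified test is.** With equal sites and exact balance within site, the ratio of true to assumed null variance is R = mean[p_s(1 − p_s)] / [p(1 − p)], where p_s are the site rates and p is their mean. The true one-sided size at 1.96 is 1 − Φ(1.96/√R). For 9/16/23%, the range of prior control rates quoted in Protocol 15.6.1 and used here only as an assumed spread between sites:

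- R = [(0.0819 + 0.1344 + 0.1771)/3] / 0.1344 = 0.976
- Size = 1 − Φ(1.96/√0.976) = 0.0236

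**3. Head-to-head simulation.** 200,000 trials per scenario, 33 per arm at each of three sites (198 in all, against 210 × 0.932 = 196). The unstratified Z is compared with the site-stratified Cochran-Mantel-Haenszel Z. Size is at 1.96. Power is for the 17.6-point difference at the final bound of 2.03, as a single look. Coverage is of the unadjusted 95% interval under no effect.

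| Assumed control rates | R | Size, unstratified | Size, stratified | Power, unstratified | Power, stratified | Coverage |
|---|---|---|---|---|---|---|
| 16/16/16% | 1.000 | 0.0248 | 0.0244 | 80.8% | 80.9% | 94.9% |
| 12/16/20% | 0.992 | 0.0247 | 0.0247 | 80.7% | 80.9% | 95.0% |
| 9/16/23% | 0.976 | 0.0240 | 0.0247 | 81.0% | 81.5% | 95.1% |
| 6/16/26% | 0.950 | 0.0227 | 0.0247 | 81.4% | 82.4% | 95.5% |
| 2/12/34% | 0.867 | 0.0176 | 0.0241 | 82.1% | 85.0% | 96.4% |

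Monte Carlo error is about √(0.8 × 0.2/200,000) = 0.1 point for power, so the first two rows show no material gain.

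**4. Incomplete blocks.** Exact balance is an idealisation. An unfinished block of 8 can leave an excess of 4 in one arm. If that happened in opposite directions at the lowest- and highest-rate sites, the unadjusted difference would shift by 4 × (0.23 − 0.09)/99 = 0.6 point, or 4 × (0.26 − 0.06)/99 = 0.8 point at the wider spread. A stratified estimate removes this.

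**5. The random site effect.** With 2 degrees of freedom, chi-square limits for a between-site variance run from 2/7.38 = 0.27 to 2/0.0506 = 39.5 times the estimate. In simulated trials of the size above, with the treatment effect present, a moment estimate of that variance was zero or negative in about 44% of trials at 12/16/20%, 20% at 9/16/23% and 5% at 6/16/26%. The SAP does not specify the model, so these figures are an approximation.

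**The case against.** The strongest reply is that a prespecified unadjusted Pearson test is legitimate. It is unbiased apart from chance imbalance, its error is on the safe side, and it delivers the planned power. Protocol 15.5 says that an interim analysis has already been done, and the SAP's table of changes states that the statistical tests are unchanged. Replacing the confirmatory statistic after data have been examined would carry a real cost for little gain. At 28.6% of the data there would be only about 20 participants per site (0.286 × 210 / 3), and a sparse-data rule for a stratified test would be needed. SAP 1.5 is presented as a sensitivity analysis for variability, not as a way to recover power. A zero variance estimate is common mainly when sites hardly differ, and then there is little to adjust for.

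All of that stands, and it argues against changing the primary test. It does not answer the narrower point. The SAP contains no unconditional overall estimate with site as fixed strata, and it omits without comment the one site-standardised summary that the protocol had.

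A reader might also infer that site is otherwise ignored. It is not: SAP 1.1.3 tests the interaction. But an interaction test with site-specific estimates is not an overall adjusted effect.

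**Conclusion.** The concern holds as a modest, inexpensive improvement. The primary test and interval do not use the factor that the randomisation controls, and the planned site-adjusted check is poorly suited to three sites. Stratifying gains about 0.5 point of power at 9/16/23%, 1 point at 6/16/26% and 3 points at 2/12/34%, and essentially nothing if sites are alike.

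Three stronger readings are not supported:
- That ignoring the blocking inflates false positives. The simulated size falls from about 0.025 to between 0.024 and 0.018 in the three wider spreads.
- That the trial is underpowered because of this. The stated 80% reproduces without stratification.
- That stratified power set against a flat 80% measures the gain. Blocking reduces the variance of the unstratified statistic too: at 6/16/26% the fair comparison is 82.4% with 81.4%, not with 80%.

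These sizes rest on assumed site rates, equal site sizes, exact balance within site, a common risk difference, and a single look at the final bound rather than the full sequential design. The documents give no site-specific rates.

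**What to change.** - **SAP 1.1.1:** keep the Z-test and its critical values as the confirmatory analysis. Beside it, prespecify a site-stratified Mantel-Haenszel test and the Mantel-Haenszel risk difference with a stratified 95% interval, and an exact stratified version under the existing sparse-data rule. Name the variance formula: the plain plug-in stratified interval, with sites weighted by size, covered 94.4% to 94.5% under no effect in the same simulations, so one with a small-sample correction is preferable.
- **SAP 1.5:** replace the random effect for site with fixed site strata (three levels), and state the model to be used for the primary outcome.
- **SAP 1.1.3 and Protocol 15.1:** reconcile the site-standardised summary. Either restore it in the SAP or list its removal, with a reason, in the table of changes.

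The cost is a few sentences and one extra analysis to report. Site is known for every participant, and neither the sample size of 210 nor the stopping bounds need change.
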